14.4. Appendix 4: Derived and Transformed Data

14.4.1. General

Multiple Measurements at One Time Point

 May arise when unscheduled visits are re-assigned to a nominal visit (see Section 14.3.2). If there is data at the nominal visit, the nominal visit data will be used in the summary tables and figures. All assessments will be listed. Subjects having both High and Low values for Normal Ranges at any post-baseline visits for safety parameters will be counted in both the High and Low categories of “Any visit post-baseline” row of related summary tables. This will also be applicable to relevant Potential Clinical Importance summary tables.
Study Day

 Calculated as the number of days from first dose of mepolizumab at Visit 2: 
 Ref Date = Missing → Study Day = Missing Ref Date < Visit 2 Date → Study Day = Ref Date – Visit 2 Date Ref Date ≥ Visit 2 Date → Study Day = Ref Date – (Visit 2 Date) + 1

14.4.2. Study Population

Demographics
Age

 GSK standard IDSL algorithms will be used for calculating age where birth day and month will be imputed ‘30th June’. Birth date will be presented in listings as ‘YYYY’. Age will be calculated relative to the date of the screening visit (Visit 1).
Body Mass Index (BMI)

 Calculated as Weight (kg) / [Height (m)]²
Disease Duration

 Calculated in years as Number of Years + (Number of Months)/12
Extent of Exposure

 Number of months of exposure to liquid mepolizumab during this study will be calculated based on the formula: Duration of Exposure (Months) = (Date of Last Dose of Study Treatment – Date of First Dose of Study Treatment + 29) * 12/365.25

14.4.3. Evaluation of Safety Syringe

Time from removal of safety syringe from storage to injection

 Calculated in minutes as Time of Injection – Time Syringe Removed from Storage

14.4.4. Safety

Adverse Events
Drug Related AEs
AEs with relationship marked 'YES' or relationship missing.
AEs Leading to Permanent Discontinuation from Study Treatment or Withdrawal from the Study
AEs with action marked "Study treatment withdrawn" or withdrawn from study status marked "YES", or a response to either of these questions is missing.
AE Time Since First Dose (Days)

 • If AE start date < Date of first dose of study treatment then Time since first dose = Date of first dose of study treatment – AE start date • If AE start date ≥ Date of first dose of study treatment then Time since first dose = AE start date – Date of first dose of study treatment + 1 • Missing if AE start date or date of first dose of study treatment is missing.
AE Duration (Days)

 • AE end date – AE start date + 1 • Missing if AE start date or end date is missing.
AEs of Special Interest

 • See Section 11.1.1

14.5. Appendix 5: Premature Withdrawals & Handling of Missing Data

14.5.1. Premature Withdrawals

Element	Reporting Detail
General	
 • Subject study completion is defined as completion of the End of Study (Week 12) visit. • Withdrawn subjects will not be replaced in the study. • All available data from subjects who were withdrawn from the study will be listed and all available planned data will be included in summary tables and figures, unless otherwise specified.
Pre-Screen and Screen Failures	
 • A subject will be assigned a subject number at the time when the informed consent form (ICF) is signed. • A subject who is assigned a subject number but does not have any screening procedures at Visit 1 will be considered a pre-screen failure. • A subject who completes at least one Visit 1 procedure but does not attempt to self-administer a dose of mepolizumab will be considered a screen failure.

14.5.2. Handling of Missing Data

Element	Reporting Detail
General	
 • In general, analysis will be performed on all available data and no imputation will be performed for missing data. However, if there are withdrawals from the study due to issues pertaining to the use of the safety syringe, a sensitivity analysis of the primary analysis will be performed. Missing or “not attempted” injection success assessments following these withdrawals will be imputed as injection failures i.e. unsuccessful attempts to self-administer mepolizumab in this sensitivity analysis. • Missing data occurs when any requested data is not provided, leading to blank fields on the collection instrument. These data will be indicated by the use of a “blank” in subject listing displays, unless all data for a specific visit are missing in which case the data is excluded from the listing. • Data below the limit of quantification (BLQ) is not missing data and must be displayed as such and included in all listings and summaries.
Outliers	
 • Any subjects excluded from the summaries and/or statistical analyses because their values are considered outliers will be documented along with the reason for exclusion in the clinical study report.

14.5.3. Handling of Missing and Partial Dates

Element	Reporting Detail
General	
 ● Partial dates will be displayed as captured in subject listing displays.
Adverse Events	
 ● Any partial dates for AEs will be raised to data management. If the full date cannot be ascertained, the following assumptions will be made: 
 ○ If the partial date is a start date, a '01' will be used for the day and 'Jan' will be used for the month. ○ However, if this imputation results in a date prior to the first dose of mepolizumab and the event could possibly have occurred during treatment from the partial information, then the date of the first dose of mepolizumab will be assumed to be the start date. ○ The event will then be considered to start on-treatment (worst case). ○ If the partial date is a stop date, a '28/29/30/31' will be used for the day (dependent on the month and year) and 'Dec' will be used for the month. ● Completely missing start or end dates will remain missing, with no imputation applied. Consequently, time to onset and duration of such events will be missing. AEs with completely missing start dates will be considered to start on-treatment (worst case). ● The recorded partial date will be displayed in listings.

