11.1. Overview of Planned Adverse Event Analyses

Table 6 provides an overview of the planned analyses of AE data. Full details of the data displays to be presented are given in Appendix 8: List of Data Displays.

Table 6 Overview of Planned Adverse Event Analyses

Endpoint / Parameter/ Display Type	Absolute		
	Summary		Individual
	T	F	L
Adverse Events (AEs)			
All AEs by SOC	Y		Y
Common AEs by Overall Frequency ^[1]	Y		
No. of Subjects & No. of Occurrences of Common AEs by SOC and PT ^[1]	Y		
All AEs by SOC and Maximum Intensity	Y		
All Drug-Related AEs by SOC	Y		
All Drug-Related AEs by SOC and Maximum Intensity	Y		
AEs by Week 12/Early Withdrawal Binding Antibody Result (see Section 12)	Y		
AEs Leading to Permanent Discontinuation of Study Treatment or Withdrawal from Study by Overall Frequency	Y		Y
AEs reported on the Day of Dosing ^[2]	Y		Y
Subject Numbers for Individual AEs			Y
Relationship Between AE SOC, PT & Verbatim Text			Y
Serious AEs (SAEs) and Other Significant AEs			
Fatal SAEs by Overall Frequency	Y		Y
All SAEs by SOC	Y		
Non-Fatal SAEs			Y
Reasons for Considering as a SAE			Y
Drug-Related Fatal SAEs by Overall Frequency	Y		
Drug-Related SAEs by SOC	Y		
No. of Subjects & No. of Occurrences of All SAEs	Y		
Adverse Events of Special Interest (AESI)			
Anaphylaxis	Y		Y
Systemic Reactions – Allergic (Type I Hypersensitivity) and Other Systemic	Y		Y
Systemic Reactions – Allergic (Type I Hypersensitivity)	Y		Y
Systemic Reactions – Other Systemic	Y		Y
Local Injection Site Reactions	Y		Y
Opportunistic Infections	Y		Y
Malignancies	Y		Y
Serious Cardiac, Vascular and Thromboembolic Events	Y		Y
Serious Ischemic Events	Y		Y

NOTES :

- T = Table, F = Figure, L = Listing, Y = Yes display generated, SOC = System Organ Class, PT = Preferred Term.
- Summary = Represents TFL related to any summaries (i.e. descriptive statistics) of the observed raw data.
- Individual = Represents FL related to any displays of individual subject observed raw data.

^[1] Common AEs will be defined as AEs with frequency $\geq 3\%$ (prior to rounding to nearest percent) in either the Total Liquid or Lyophilised Vial treatment groups.

^[2] AEs reported on the day of dosing will be defined as adverse events with a start date equal to the date of dosing.

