14.8.6. Safety Analyses

CONFIDENTIAL

205667

No.	Population	IDSL / TST ID / Example Shell	Title	Programming Notes	Deliverable [Priority]
Safety : Tables					
Adverse Events					
11.1	All Subjects	AE1	Summary of All On-Treatment Adverse Events by System Organ Class and Preferred Term		SAC
11.2	All Subjects	AE1	Summary of All Post-Treatment Adverse Events by System Organ Class and Preferred Term		SAC
11.3	All Subjects	AE3	Summary of Common (>=3% Incidence) On-Treatment Adverse Events by Overall Frequency		SAC
11.4	All Subjects	AE15	Summary of Common (>=3% Incidence) On-Treatment Adverse Events by Preferred Term (Number of Subjects and Occurrences)		SAC
11.5	All Subjects	AE5A	Summary of All On-Treatment Adverse Events by Maximum Intensity by System Organ Class and Preferred Term		SAC
11.6	All Subjects	AE1	Summary of All Drug-Related Adverse Events by System Organ Class and Preferred Term		SAC
11.7	All Subjects	AE5A	Summary of All Drug-Related Adverse Events by Maximum Intensity by System Organ Class and Preferred Term		SAC
11.8	All Subjects	AE1	Summary of On-Treatment Adverse Events by Week 12 Binding Antibody Result	Add in row with n in each binding antibody result category. See Section 12.	SAC
11.9	All Subjects	AE3	Summary of All Adverse Events Leading to Permanent Discontinuation from Study Treatment and/or Withdrawal from the Study by Overall Frequency		SAC

CONFIDENTIAL

205667

No.	Population	IDSL / TST ID / Example Shell	Title	Programming Notes	Deliverable [Priority]
Safety : Tables					
11.10	All Subjects	AE1	Summary of Adverse Events Reported on the Day of Dosing by System Organ Class and Preferred Term		SAC
11.11	All Subjects	AE7	Listing of Subject Numbers for Individual On-Treatment Adverse Events		SAC
11.12	All Subjects	AE2	Listing of Relationship of Adverse Event, System Organ Classes, Preferred Terms and Verbatim Text		SAC
Serious Adverse Events					
11.13	All Subjects	AE3	Summary of Fatal Serious Adverse Events by Overall Frequency		SAC
11.14	All Subjects	AE3	Summary of Drug-Related Fatal Serious Adverse Events by Overall Frequency		SAC
11.15	All Subjects	AE1	Summary of All On-Treatment Serious Adverse Events by System Organ Class and Preferred Term		SAC
11.16	All Subjects	AE16	Summary of All On-Treatment Serious Adverse Events by System Organ Class and Preferred Term (Number of Subjects and Occurrences)		SAC
11.17	All Subjects	AE1	Summary of All Post-Treatment Serious Adverse Events by System Organ Class and Preferred Term		SAC

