20	All Subjects	AE8	Listing of Adverse Events Reported on the Day of Dosing	Add phase: Pre-treatment, on-treatment, post-treatment (see Section 14.2.1.1).	SAC

ICH and Other Listings					
No.	Population	IDSL / TST ID / Example Shell	Title	Programming Notes	Deliverable [Priority]
Serious Adverse Events					
21	All Subjects	AE8	Listing of Fatal Serious Adverse Events	Add phase: Pre-treatment, on-treatment, post-treatment (see Section 14.2.1.1).	SAC
22	All Subjects	AE8	Listing of Non-Fatal Serious Adverse Events	Add phase: Pre-treatment, on-treatment, post-treatment (see Section 14.2.1.1).	SAC
23	All Subjects	AE14	Listing of Reasons for Considering as a Serious Adverse Event		SAC
Adverse Events of Special Interest					
24	All Subjects	AE8	Listing of Adverse Events Reported by the Investigator as Meeting the Criteria for Anaphylaxis	Add phase: Pre-treatment, on-treatment, post-treatment (see Section 14.2.1.1). Add injection reaction symptoms and number of doses prior to event.	SAC
25	All Subjects	AE8	Listing of Adverse Events Defined by the Investigator as Systemic Reactions - Allergic (Type I Hypersensitivity)	Add phase: Pre-treatment, on-treatment, post-treatment (see Section 14.2.1.1). Add injection reaction symptoms and number of doses prior to event.	SAC
26	All Subjects	AE8	Listing of Adverse Events Defined by the Investigator as Systemic Reactions – Other Systemic	Add phase: Pre-treatment, on-treatment, post-treatment (see Section 14.2.1.1). Add injection reaction symptoms and number of doses prior to event.	SAC

ICH and Other Listings					
No.	Population	IDSL / TST ID / Example Shell	Title	Programming Notes	Deliverable [Priority]
27	All Subjects	AE8	Listing of Adverse Events Defined by the Investigator as Local Injection Site Reactions	Add phase: Pre-treatment, on-treatment, post-treatment (see Section 14.2.1.1). Add injection reaction symptoms and number of doses prior to event.	SAC
28	All Subjects	AE8	Listing of Adverse Events Categorised as Serious Cardiac, Vascular and Thromboembolic Events	Add phase: Pre-treatment, on-treatment, post-treatment (see Section 14.2.1.1).	SAC
29	All Subjects	AE8	Listing of Adverse Events Categorised as Serious Ischemic Events	Add phase: Pre-treatment, on-treatment, post-treatment (see Section 14.2.1.1).	SAC
30	All Subjects	AE8	Listing of Adverse Events Categorised as Malignancies	Add phase: Pre-treatment, on-treatment, post-treatment (see Section 14.2.1.1).	SAC

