		Liquid Safety Syringe (N=XX)
1	All Events >= 1 event [1]	xx/xx (x%)
	1 event	xx (x%)
	2 events	xx (x%)
	3 events	xx (x%)
	>=4 events	xx (x%)
2	Serious Events >= 1 event [1]	xx/xx (x%)
3	Events considered related to investigational product >= 1 event [1]	xx/xx (x%)
4	Intensity [1]	
	Mild	xx/xx (x%)
	Moderate	xx/xx (x%)
	Severe	xx/xx (x%)
5	Outcome [1]	
	Recovered/Resolving	xx/xx (x%)
	Recovering/Resolving	xx/xx (x%)
	Not recovered/Not Resolved	xx/xx (x%)
	Recovered/Resolved with sequelae	xx/xx (x%)
	Fatal	xx/xx (x%)

[1] Information presented as number of events / number (%) subjects with at least one event. Subjects may be counted in more than one row.

[2] Cardiac History=Yes includes all subjects with any past medical condition under Cardiac Disorders.

[3] Unable to categorise time since last dose as event time not reported.

userid: /arenv/arprod/compound/study/final/drivers/drivename.sas DDMMYYYY HH:MM

Example TAB_S1 (Cont.)
 Protocol: MID205667
 Population: All Subjects (Safety)

Table X.X

Summary Profile of On-Treatment Adverse Events Defined by the Investigator as Allergic (Type I Hypersensitivity) Reactions

		Liquid Safety Syringe (N=XX)
6	Action Taken [1]	
	Study treatment withdrawn	xx/xx (x%)
	Dose reduced	xx/xx (x%)
	Dose increased	xx/xx (x%)
	Dose not changed	xx/xx (x%)
	Dose interrupted/delayed	xx/xx (x%)
	Not applicable	xx/xx (x%)
7	Cardiac History [1][2]	
	Yes	xx/xx (x%)
	No	xx/xx (x%)
8	Anaphylaxis Criteria Met	
	Anaphylactic Criterion 1	xx/xx (x%)
	Anaphylactic Criterion 2	xx/xx (x%)
	Anaphylactic Criterion 3	xx/xx (x%)
9	No. doses prior to event [1]	
	1	xx/xx (x%)
	2	xx/xx (x%)
	3	xx/xx (x%)
	etc.	
10	No. doses prior to first event	
	1	xx (x%)
	2	xx (x%)
	3	xx (x%)
	etc.	

[1] Information presented as number of events / number (%) subjects with at least one event. Subjects may be counted in more than one row.

[2] Cardiac History=Yes includes all subjects with any past medical condition under Cardiac Disorders.

[3] Unable to categorise time since last dose as event time not reported.

userid: /arenv/arprod/compound/study/final/drivers/drivername.sas DDMMYYYY HH:MM

Example TAB_S1 (Cont.)
 Protocol: MID205667
 Population: All Subjects (Safety)

Table X.X

Summary Profile of On-Treatment Adverse Events Defined by the Investigator as Allergic (Type I Hypersensitivity) Reactions

	Liquid Safety Syringe (N=XX)
11	Time since last dose to event onset [1]
	<=1 hr xx/xx (x%)
	1-<6 hrs xx/xx (x%)
	6-<24 hrs xx/xx (x%)
	>=24 hrs xx/xx (x%)

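### Imputed AE start dates are not kept out of the day-of-dosing and dose-number displays, so some partially dated AEs would be counted on the first-dose day or on too early a dose

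*SAP*

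**What the plan says.** SAP 14.5.3 sends partial AE dates to data management first. Where the full date cannot be found, "If the partial date is a start date, a '01' will be used for the day and 'Jan' will be used for the month". The override applies "if this imputation results in a date prior to the first dose of mepolizumab and the event could possibly have occurred during treatment"; in that case "then the date of the first dose of mepolizumab will be assumed to be the start date", which the SAP labels a worst case. Completely missing dates are not imputed. Listings show the date as recorded.

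Two groups of displays depend on the AE start date:

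- **Day of dosing.** SAP 11.1, Table 6 note 2: "AEs reported on the day of dosing will be defined as adverse events with a start date equal to the date of dosing". This feeds Table 11.10, "Summary of Adverse Events Reported on the Day of Dosing by System Organ Class and Preferred Term", and Listing 20.
- **Dose number.** TAB_S1 sections 9 and 10 count doses before the event for all AEs of special interest. For Listings 24-27 the programming note is "Add injection reaction symptoms and number of doses prior to event".

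Neither group carries an exclusion for imputed dates.

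**The concern.** As a worst case, the imputation makes sense for treatment phase: an event that might have been on treatment is treated as such. Nothing confines it to that use. SAP 14.2.1.1 already classes a partially dated AE as on-treatment unless there is contrary evidence, so phase does not need an imputed date. SAP 14.5.3 makes time to onset and duration missing only when a date is completely missing, and SAP 14.4.4 does the same for time since first dose. Both imply that imputed partial dates are carried into date-based derivations.

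The affected displays are those that tie an event to a particular injection of the new presentation. An imputed date there can produce a same-day event at dose 1 that did not occur on that day, or credit an event after dose 2 or 3 to an earlier dose. In summary tables, a reader could not tell these entries from recorded ones.

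**Working it through.** The plan gives no figure on this point, so there is none to reproduce.

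**Inputs**
- Three doses at 4-week intervals (Protocol 4.1): nominal days 0, 28 and 56.
- AEs collected from Visit 2 to the End of Study visit (Protocol 7.7.1.1): nominal days 0 to 84, or 85 possible onset days.
- Imputation rule from SAP 14.5.3; day-of-dosing definition from SAP Table 6 note 2.
- Doses before event = number of dose dates on or before the start date. The SAP gives no formula; this is the natural reading.
- Assumptions: nominal spacing, onset equally likely on each day, first dose on each of the 365 days of 2017.

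**Direction of the dose count.** The imputed date is never later than the true onset: it is either the 1st of the period containing the onset, or the first-dose date, which precedes any collected AE or falls on the same day. The dose count can therefore only stay the same or fall.

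**Example** (doses 15 March, 12 April, 10 May 2017; day missing)

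| True onset | Imputed | Result |
|---|---|---|
| 28 March | 15 March | False day-of-dosing AE |
| 5 April | 1 April | Dose 1, correct |
| 20 April | 1 April | Dose 1 instead of dose 2 |
| 20 May | 1 May | Dose 2 instead of dose 3 |
| 3 June | 1 June | Dose 3, correct |

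**Enumeration, day missing only.** 365 × 85 = 31,025 cases.
- Moved to first-dose date: 5,373 / 31,025 = 17.3%. All meet the day-of-dosing definition.
- Truly on a dosing day: 3 × 365 = 1,095; 1,095 / 31,025 = 3.5%.
- Day-of-dosing after imputation: 1,095 + 6,021 false − 666 lost = 6,450; 6,450 / 31,025 = 20.8%. False additions are 19.4% and losses 2.1%.
- Placed on an earlier dose: 10,714 / 31,025 = 34.5%; on a later dose: 0.
- Among events after dose 2 or 3: 10,714 / 20,805 = 51.5% on an earlier dose.
- Among events in a calendar month after the first-dose month: 10,660 / 25,287 = 42.2%. About 19% of these events fall in a month with no dose.
- At least one error (false day-of-dosing or wrong dose): 16,692 / 31,025 = 53.8%, so 46.2% have neither.

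**Sensitivity**

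| Scenario | Day-of-dosing, true → imputed | Earlier dose | At least one error |
|---|---|---|---|
| Day missing, uniform onset | 3.5% → 20.8% | 34.5% | 53.8% |
| Day missing, onset within days 0-6 of a dose | 14.3% → 33.3% | 57.9% | 85.1% |
| Day and month missing, uniform onset | 3.5% → 88.8% | 64.3% | 95.1% |

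**Scale.** The percentages are shares of partially dated AEs, not of all AEs. Ten day-missing AEs would give about two false day-of-dosing entries (10 × 0.194) and three to four on too early a dose (10 × 0.345). In a table of subjects with N = 55, one misplaced AE changes a row by at most 1/55 = 1.8 percentage points, and by nothing if the subject is already counted there.

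**The case against.** Several points on the other side stand.

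- **Safeguards.** Partial dates are queried first, and listings show the recorded date, so a reader of Listings 20 and 24-27 can see that a date is incomplete. Anaphylaxis, systemic reactions and injection site reactions are collected on targeted eCRF pages. Few dates may remain partial. The summary tables have no such marker.
- **The use is inferred.** The SAP does not say outright that imputed dates feed Table 11.10 or the dose counts. The reading rests on its definitions, supported by SAP 14.2.1.1 and the time-to-onset wording in 14.5.3.
- **TAB_S1 covers on-treatment events only.** SAP 14.2.1.1 ends that phase 28 days after the first dose. As written, this removes later fully dated events from TAB_S1, so the size of the dose-count effect in that table depends on how the window is settled. Listings 24-27 show all phases.

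A reader might also infer more than the documents support:

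- That every partially dated AE is misplaced. With only the day missing, about 46% have neither error.
- That the rule creates same-day reactions. Table 11.10 covers all AEs, and whether an AE is a reaction comes from the investigator's entry, which imputation does not change.
- That the error understates risk in both displays. In Table 11.10 the net error is upward (19.4% added, 2.1% lost), in line with the worst-case intent. The dose count has no such conservative direction.
- That TAB_S1 contradicts itself because it has a missing row footnoted "Unable to categorise time since last dose as event time not reported". That row concerns hours since the last dose, which needs a clock time; counting doses does not. It is a useful model for a new row, not an inconsistency.

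**Conclusion.** The point holds as a minor defect of specification. Read literally, SAP 14.5.3 and Table 6 note 2 together count every AE moved to the first-dose date as a day-of-dosing AE, and the dose count can be wrong only towards an earlier dose. With only the day missing, the effect on partially dated AEs is substantial under the stated assumptions, and it is larger when the month is missing too. Actual visit windows and clustering of onset would change the percentages; the direction of the dose-count error would not change.

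The effect on the report is unknown, because the number of dates left partial after query is not given and may be small in about 55 subjects. The trial is single-arm and descriptive, and the primary endpoint does not use AE dates.

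**What to change.** - In SAP 14.5.3, state that imputed start dates are not used to determine day-of-dosing status or dose number.
- In Table 11.10 and Listing 20, show partially dated AEs that could have started on a dosing day in a separate 'date incomplete' row or flag. They should be neither dropped nor counted as confirmed: restricting the table to complete dates would remove true same-day events from a safety display.
- Add a 'Missing/partial date' category to TAB_S1 sections 9 and 10 and to the dose count in Listings 24-27.

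The cost is one sentence and a few rows or flags in the display specifications. No data are lost. The downside is that a few true same-day events would appear as 'date incomplete'.
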